# 4.2 PRIMARY ENDPOINT - SAFETY

The study's primary safety endpoint is incidence of adjudicated Serious Adverse Events (SAE), which is a composite of:

- Mortality through 48 hours after the index procedure related to FlowTriever2 Catheter
- Major bleeding through 48 hours after the index procedure related to FlowTriever2 Catheter
- Intra-procedural device or procedure-related adverse events, including:
  - Clinical deterioration defined by hemodynamic or respiratory worsening
  - Pulmonary vascular injury related to FlowTriever2 Catheter
  - Cardiac injury related to FlowTriever2 Catheter

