Mechanical thrombus retrieval from the pulmonary arteries can, in theory, result in dispersion of some residual thromboembolic material distal to the central obstruction to the periphery of the lungs. With fragmentation devices, the fundamental objective is to eliminate central thrombi and fragment them so that they migrate to more distal branches, thus alleviating main pulmonary obstruction, which allows both an improved perfusion and a reduction of elevated pulmonary arterial pressures right ventricular pressure overload. Worsening of hemodynamic parameters due to distal embolization can occur, however, available clinical data does not associate serious adverse sequelae due to distal embolization in PE patients treated with fragmentation devices. Since the primary mode of action of the FlowTriever2 Catheter is clot retrieval, the potential for distal showering of thromboemboli does exist, but with the synchronized thrombus removal mechanism of the FlowTriever2 Catheter and aspiration capability of the Triever Catheter, it is anticipated to occur less frequently and to a lesser degree than devices that rely solely upon fragmentation. The minimal risk of distal embolization is outweighed by the anticipated benefits of the FlowTriever2 Catheter in the acute relief of the pulmonary arterial emboli.

Finally, while the intent of FlowTriever2 intervention is not to remove the entire embolic load, the risk of clot remaining after the embolectomy procedure is mitigated by the physician's ability to deliver thrombolytic to enhance both the impact of clot extraction and the body's natural lytic system. Future thrombolytic therapy is not precluded following FlowTriever2 treatment.

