## 8.2.1 ADVERSE DEVICE EFFECT (ADE)

An adverse device effect (ADE) is an AE related to the use of an investigational medical device. (ISO 14155:2020 3.1)

**NOTE 1**: This definition includes adverse events resulting from insufficient or inadequate instructions for use, deployment, implantation, installation, or operation, or any malfunction of the investigational medical device.

**NOTE 2**: This definition also includes any event from use error or from intentional misuse of the investigational medical device. (ISO 14155:2020 3.1)

NOTE 3: This includes 'comparator' if the comparator is a medical device. (ISO 14155:2020, 3.1)

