## 8.4 EVENT RELATIONSHIP

The Investigator will categorize the relationship of the adverse event as follows:

- **Study Disease-related:** Event is clearly attributable to underlying disease state with no temporal relationship to the device, treatment or medication.
- **Concomitant Disease-related:** Event is attributable to disease other than the study disease with no temporal relationship to the device, treatment or medication.
- **Procedure-related:** Event has a strong temporal relationship to the procedure or treatment with the device deployment or any user handling.
- **Device-related:** Event has a strong temporal relationship to the device and alternative etiology is less likely.
  - Primary Study Device: FlowTriever2 Catheter

FLARE-FT2 Study CONFIDENTIAL Page 41 of 60

- Ancillary Device: Any device other than the FlowTriever2 Catheter, such as the Triever Catheter, a
  guidewire, pressure monitoring catheter, or infusion catheter
- o **Device Unknown:** Device-related but unable to attribute a specific device relationship
- **tPA-related:** Event is clearly attributable to tPA medication with no temporal relationship to the device or treatment.
- Unrelated to the above categories: Event has no relationship to any of the above-mentioned categories.
- **Unknown:** Event relationship is not known or unsure.

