5.5. Secondary Effectiveness Endpoint Analysis

The secondary effectiveness endpoint analysis is performed by assessing the means, standard deviations, medians, and inter-quartile ranges of the systolic pulmonary arterial pressure changes and/or percentage change between pre- and post-procedure. Adjunctive thrombolytic use is reported as numbers and percentages.

6. Terms and Definitions

Term	Definition
Primary Safety Definitions	
Clinical Deterioration	Clinical deterioration will include treatment-related events, such as unplanned endotracheal intubation, unexpected requirement for mechanical ventilation, arterial hypotension (>1 hour or requiring vasopressors) or shock, cardiopulmonary resuscitation, persistent worsening in oxygenation, and emergency surgical embolectomy.
Device Related Death	Device-related death is defined as any death directly related to the device not performing as expected. Device-related death would include death from: 
 • Vascular or cardiovascular injury • Device malfunction • Device-induced cardiac arrhythmia
Life Threatening or Disabling Bleeding (VARC-2)	
 • Fatal bleeding, OR • Bleeding in a critical organ, such as intracranial, intraspinal, intraocular, or pericardial necessitating pericardiocentesis, or intramuscular with compartment syndrome, OR • Bleeding causing hypovolemic shock or severe hypotension requiring vasopressors or surgery, OR • Overt source of bleeding with drop in hemoglobin ≥ 5 g/dL or whole blood or packed red blood cells (RBCs) transfusion ≥ 4 units*
Major Bleeding (VARC- 2)	Overt bleeding that is: 
 • Associated with a drop in the hemoglobin level of at least 3 g/dL, OR • Requires transfusion of 3 units of whole blood/RBC, OR • Causes hospitalization, permanent injury, or requiring surgery, AND • Does not meet criteria of life-threatening or disabling
Minor Bleeding (VARC- 2)	Any bleeding worthy of clinical mention (e.g., access site hematoma) that does not qualify as life-threatening or disabling bleeding or major bleeding.
Pulmonary Vascular Injury	Pulmonary vascular injury is defined as perforation or injury of a major pulmonary arterial branch during the index procedure requiring intervention, including but not limited to blood transfusion, open or endovascular intervention, to avoid permanent injury.

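### The definition of device-related death conflicts with itself and with the endpoint text, so some FlowTriever2-related deaths within 48 hours could be left out of the primary safety composite

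*SAP*

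**What the plan says.** Protocol 4.2 and 9.3 and SAP 2.1 word the mortality component identically: "Mortality through 48 hours after the index procedure related to FlowTriever2 Catheter". No condition is placed on how the device performed. SAP 5.2 shortens this to device-related mortality.

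Protocol 12 and SAP 6 both define Device Related Death under the subheading for primary safety definitions: "Device-related death is defined as any death directly related to the device not performing as expected". The next sentence says that such death would include death from three causes. These are "Vascular or cardiovascular injury", device malfunction, and "Device-induced cardiac arrhythmia".

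Two other rules bear on the same question. Protocol 8.4 classes an event as device-related on this test: "Event has a strong temporal relationship to the device and alternative etiology is less likely". It has a separate category for the FlowTriever2 Catheter as the primary study device. On adverse device effects, Protocol 8.2.1 states: "This definition also includes any event from use error or from intentional misuse of the investigational medical device". Protocol 12 and SAP 6 repeat that inclusion in nearly the same words.

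Protocol 8.7 gives the CEC the final word on relatedness. All-cause mortality and device-related SAEs through the 30-day visit are secondary safety endpoints (Protocol 4.4, SAP 2.3).

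**The concern.** A safety endpoint has to count deaths caused by a device that is used as intended and works as intended, as well as deaths from device failure. The lead sentence of the definition points to failure only. The endpoint text, the relatedness rule and the adverse device effect definition all point to causation. The CEC has to apply one of these, and neither document says which.

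The protocol itself names a mechanism that needs no malfunction. Section 7.1.4 says that "the potential for distal showering of thromboemboli does exist" and that hemodynamics can worsen as a result. Section 7.1.1 lists distal embolism and air embolism among the possible complications. None of these is a listed cause of device-related death.

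At stake is whether the gravest component of the primary composite is counted by one rule. Without that, the same death could be device-related in a secondary endpoint and not in the primary one.

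**Working it through.** **1. The rules side by side**

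| Place | Test applied | Must the device underperform? |
|---|---|---|
| Protocol 4.2, 9.3; SAP 2.1 | Related to the FlowTriever2 Catheter | No |
| Protocol 12, SAP 6, lead sentence | Death tied to device performance | Yes |
| Protocol 12, SAP 6, listed causes | Injury, malfunction or arrhythmia (open list) | Only for the malfunction item |
| Protocol 8.4 | Timing, with another cause less likely | No |
| Protocol 8.2.1, 12; SAP 6 (adverse device effect) | Related to device use, including use error and misuse | No |

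The definition disagrees with itself (rows 2 and 3), and its lead sentence disagrees with every other row.

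**2. Four deaths within 48 hours, taken through the rules**

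- *Fatal vascular or cardiac injury, or device-induced arrhythmia, with a normally working or misused catheter.* The lead sentence says no, but the listed causes say yes. It would probably count.
- *Intra-procedural shock or resuscitation that is device- or procedure-related, followed by death.* It enters the composite as clinical deterioration, whatever the death definition says.
- *Distal or air embolism with a normally working catheter, no qualifying event during the procedure, then decompensation and death at, say, hour 10.* Protocol 8.4 is met if the CEC finds other causes less likely. The lead sentence is not met and the cause is not listed. No other component catches it, because deterioration counts only if intra-procedural.
- *Fatal bleed after the procedure.* The VARC-2 entry for major bleeding excludes bleeding that meets the life-threatening criteria, and those include fatal bleeding. The bleeding component therefore misses it. It can enter only through the mortality component, for instance if judged a vascular injury.

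The third and fourth cases are the gap.

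**3. Size**

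Inputs from SAP 5.1: n = 50, assumed rate 11%, performance goal 25%, one-sided alpha 0.05, power at least 80%.

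The plan's own figure first. With an exact one-sample binomial test, the goal is met with 7 or fewer events: P(X ≤ 7 | 0.25) = 0.0453, and P(X ≤ 7 | 0.11) = 0.8207. The stated power is reproduced. Rewording the definition changes none of these inputs.

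Effect of one omitted death that enters by no other component: 1/50 = 2.0 percentage points. The exact one-sided 95% upper limit solves P(X ≤ x | p) = 0.05:

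| Events with the death counted | Events with it omitted |
|---|---|
| 1/50 = 2.0%, upper limit 9.1% | 0/50 = 0%, upper limit 5.8% |
| 8/50 = 16.0%, upper limit 27.0% | 7/50 = 14.0%, upper limit 24.7% |

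The documents give no rate for such deaths. If it were 1%, 2% or 3% (assumption), the chance of at least one in 50 subjects is 1 − (1 − d)^50 = 39%, 64% or 78%.

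**The case against.** The best defence is that the definition is badly worded but does little harm. Each part has some force.

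- *The list is illustrative.* A CEC could read right heart failure after embolism as cardiovascular injury and count it. This stands as a possibility, but inclusion would then rest on how one term is stretched.
- *The endpoint text has no performance condition.* Applying Protocol 8.4, with its category for the FlowTriever2 Catheter, is at least as natural a reading. This also stands. Against it, the narrower entry sits under the primary safety definitions, and SAP 5.2 uses the matching term.
- *The protocol does not predict serious harm from distal embolization.* Section 7.1.4 calls the risk minimal and says that available data on fragmentation devices show no serious sequelae. This is correct, and it bears on how often the gap would be used. It does not close the gap.
- *The death would still be visible.* It would appear in all-cause 30-day mortality and, if judged device-related under 8.4, as a device-related SAE. Both are secondary endpoints, and the second would contradict the primary count.

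A reader might infer that every death from a normally working catheter, or from use error, is excluded. The documents do not support that. Two of the three listed causes carry no malfunction condition, and intra-procedural deterioration is caught separately.

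**Conclusion.** The point holds as an inconsistency with a narrow but real gap. Applied literally, the definition can drop a FlowTriever2-related death within 48 hours from the primary composite when two things are true: no qualifying intra-procedural event occurred, and the cause lies outside the listed examples. A fatal bleed after the procedure is exposed in the same way.

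The size is 2 percentage points per omitted death, assuming 50 subjects in the denominator and no entry through another component. How often this would happen cannot be estimated from the documents.

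A reader might go further and call one reclassified death decisive, because FLARE had no device-related major adverse events and the FLASH interim had no device-related deaths. That is too strong. SAP 2 says that the endpoints are descriptive and do not determine study success, and SAP 5.1 disclaims reliance on hypothesis testing. The move across 25% between 8 and 7 events shows scale only. What is affected is the reported count and how it is interpreted. With no formal test, that count is the result, so the wording is worth correcting.

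**What to change.** In Protocol 12 and SAP 6:

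- Delete "device not performing as expected" from the Device Related Death entry.
- State that the 48-hour mortality component is any death through 48 hours that the CEC judges related to the FlowTriever2 Catheter under Protocol 8.4, including deaths from use error and from effects of a normally working device.
- Keep the three listed causes, marked as examples.

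Report a listing of all deaths through 48 hours with the CEC attribution. Align the CEC Charter if it differs; it is not among the documents, so its wording is unknown.

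The cost is about one sentence in each document. Sample size, alpha and power are unchanged. The event count may be slightly higher. If FLARE used the narrower definition, which the documents do not say, comparison with it becomes slightly less direct. The listing of all 48-hour deaths lets a reader recount under either rule.
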